during the phone call conversation for correcting the management skills learned in the sessions in a real-world situations with their children, and questions about how would the situation would be handled next time in terms of gaining self-agency skill in child disruptive behaviour management. Pre- and post-intervention assessments were conducted to measure outcomes for each participant. Simultaneously, the control group underwent pre-testing, with post-testing conducted two months later to assess comparative outcomes.

Table 3.1Contents of group triple p sessions Adapted from (Yusuf, Ö., et al,2019).

Session number	Content	Session duration
1. Positive parenting	Working as a group What is positive parenting? Why do children behave as they do? Goals for change Keeping track Developing good relationships with children Encouraging good behaviour Teaching new skills and behaviours Managing misbehaviour Developing parenting routines Finalizing your behaviour chart Family survival tips High-risk situations Planned activities Preparing for telephone sessions Preparing for the session Update on practice Other issues	120 minutes (group)
2. Helping children develop	Developing good relationships with children Encouraging good behaviour	120 minutes (group)
3. Managing misbehaviour	Teaching new skills and behaviours Managing misbehaviour Developing parenting routines Finalizing your behaviour chart	120 minutes (group)
4. Planning ahead	Family survival tips High-risk situations Planned activities Preparing for the session Update on practice Other issues	120 minutes (group)
5. Using positive parenting strategies 1	Preparing for the session Update on practice Other issues	15–30 minutes (telephone)
6. Using positive parenting strategies 2	Preparing for the session Update on practice Other issues	15–30 minutes (telephone)
7. Using positive parenting strategies 3	Preparing for the session Update on practice Other issues	15–30 minutes (telephone)
8. Programme close	Preparing for the session Update on practice Phasing out the programme Progress review Keeping up the good changes Problem-solving for the future Future goals Final assessment	120 minutes (group)

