## **Ethical consideration**

Ethical approval for the study was obtained from the AAUP Review Board (Appendix1), and additional approval was granted by the Ministry of Health (Appendix5) for access to information from medical files. Informed consent (Appendix3) was obtained from each participant, and all outcome measures were collected anonymously. Participation in the study was entirely voluntary, with participants given the option to withdraw at any time. To ensure confidentiality, all collected data was securely stored in a locked environment accessible only to the researcher.

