## **Data Analysis**

All statistical analyses were conducted using IBM SPSS Statistics version 27. Data were first screened for completeness and accuracy. Missing data were assumed to be random of less than 3%, and were excluded using listwise deletion. Descriptive statistics (frequencies, percentages, means, and standard deviations) were used to characterize demographic variables and baseline measures. Reliability for each outcome instrument was assessed using Cronbach's alpha coefficients and intraclass correlation coefficients (ICC). Normality of continuous variables was evaluated using the Kolmogorov-Smirnov test. To assess baseline equivalence between the intervention and control groups, independent samples *t*-tests were performed on all pre-intervention variables. The effectiveness of the Triple P intervention was analyzed by comparing pre- and post-intervention scores within and between groups using independent *t*-tests. Statistical significance was determined at an alpha level of 0.05 (two-tailed). The primary analyses focused on evaluating changes in parenting practices, parental competence, and child behavior. Differences in mean change scores between the two groups were used to assess the impact of the intervention relative to standard care. Sensitivity or subgroup analysis was not conducted.

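### Within-group pre/post comparisons are assigned an independent t-test although the same mothers are measured twice; with positive pre-post correlation the test is conservative and loses power

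*Combined protocol and SAP*

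**What the plan says.** The only statement of the effectiveness test is in the Data Analysis section, which describes "comparing pre- and post-intervention scores within and between groups using independent" t-tests. One test thus serves two different comparisons: pre against post inside a group, and intervention against control. No paired t-test, repeated-measures model or other method for correlated scores is named in the document.

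The Intervention Protocol section sets out the measurement schedule: "Pre- and post-intervention assessments were conducted to measure outcomes for each participant", and "the control group underwent pre-testing, with post-testing conducted two months later". Both groups are therefore measured twice.

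The Data Analysis section also names the contrast that carries the conclusion: "Differences in mean change scores between the two groups were used to assess the impact of the intervention relative to standard care". On testing level it says "Statistical significance was determined at an alpha level of 0.05 (two-tailed"). The Ethical consideration section adds that "all outcome measures were collected anonymously". The document does not say whether or how a mother's two questionnaires were matched.

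**The concern.** Scores from the same mother on the same scale about two months apart are normally positively correlated. An independent-samples test treats the pre scores and the post scores as coming from different women, so it ignores that correlation and uses a standard error that is too large.

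The within-group comparisons are listed as part of the effectiveness analysis, so the error would reach the reported results. A real improvement in the intervention group, or a real drift in the control group, could be reported as not significant. The second case also matters for interpretation: a reader who sees significance in one arm and none in the other may take that contrast as evidence of benefit, which it is not.

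**Working it through.** **Inputs from the document.** Same mothers measured before and after in each group (Intervention Protocol); independent t-test for within-group comparisons, two-sided 5% (Data Analysis). The plan gives no figure to reproduce.

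**Inputs assumed.** n = 20, 30 or 50 mothers in a group; equal pre and post SDs, σ; pre-post correlation r = 0, 0.3, 0.5, 0.7; normal scores; true change of 0, 0.4, 0.8 or 1.0 SD.

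**Step 1: standard error.** The true variance of the mean pre-post change is 2σ²(1−r)/n. The independent test uses 2σ²/n. The ratio of standard errors is 1/√(1−r):

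- r = 0.3: 1/√0.7 = 1.20, too large by 20%
- r = 0.5: 1/√0.5 = 1.41, too large by 41%
- r = 0.7: 1/√0.3 = 1.83, too large by 83%

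**Step 2: actual type I error.** By normal approximation it is 2[1 − Φ(1.96/√(1−r))]. At r = 0.5 this is 2[1 − Φ(2.77)] = 0.0056. For r = 0.3 and 0.7 it is 0.019 and 0.0003. Simulation of the t-test itself at n = 30 (200,000 trials per cell) gives about 2.0%, 0.7% and 0.08%, against the nominal 5%. At r = 0 it gives 5.0%.

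**Step 3: power for a 0.4 SD change.** By normal approximation, with σ = 1, power of the independent test is Φ[(0.4 − 1.96√(2/n))/√(2(1−r)/n)]. At n = 30 and r = 0.5 this is Φ[(0.400 − 0.506)/0.183] = Φ(−0.58) = 28%; simulation gives 27%. The paired test has noncentrality 0.4/√(2(1−r)/n) = 0.4/0.183 = 2.19 on 29 degrees of freedom, hence power 56%. The full set, independent (simulated) against paired (exact noncentral t):

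| n | r = 0.3 | r = 0.5 | r = 0.7 |
|---|---|---|---|
| 20 | 20% v 30% | 16% v 40% | 11% v 59% |
| 30 | 30% v 43% | 27% v 56% | 23% v 78% |
| 50 | 51% v 65% | 51% v 79% | 52% v 95% |

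At r = 0 and n = 30 the two tests nearly agree (33% and 32%), so the gap comes from the ignored correlation.

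**Step 4: larger changes, n = 30.** At 0.8 SD, independent against paired power is 90% v 95%, 93% v 99% and 97% v over 99% for r = 0.3, 0.5 and 0.7. At 1.0 SD both tests exceed 98% at every r.

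**Step 5: between-group contrast.** An independent t-test on change scores, simulated at n = 30 per group with mothers independent of one another, rejects a true null in 5.1%, 5.0% and 4.9% of trials for r = 0.3, 0.5 and 0.7. It keeps its level.

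**The case against.** The strongest reply is that the contrast that decides the trial is sound. Impact is judged by the between-group difference in mean change, and an independent t-test is right for that. Within-group tests cannot establish efficacy in a controlled design, and the error makes them conservative. This stands, and it limits the weight of the point. It does not remove it, because the plan lists the within-group comparisons under effectiveness.

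Second, the sentence is compressed and may simply have lost the word paired. That is possible, and the document cannot settle it. Followed as written, though, it gives the wrong test.

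Third, the size of the loss depends on an effect that is unknown. This is fair: for changes of 0.8 to 1.0 SD the power loss at n = 30 is modest to negligible. The type I error stays below 5% whatever the effect.

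Fourth, anonymous collection may only mean de-identified, and change scores suggest that records were matched. That is likely. But a difference in mean change can be computed from unmatched group means, whereas its standard error cannot, so a sentence of clarification is still worth asking for.

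**Conclusion.** The point holds as the plan is written: an independent t-test is named for paired pre/post data, and its within-group standard errors and p-values are too large when r is positive. Under the assumed range of r, the standard error is 20% to 83% too large. At n = 30 the type I error falls to between about 2.0% and under 0.1%, and power for a 0.4 SD change is 13 to 55 percentage points lower than with a paired test (43 − 30 and 78 − 23). The direction depends on positive correlation: at r = −0.3 the test would be anti-conservative, at about 8.6% by the approximation in Step 2.

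The error is confined to the within-group results and leaves the between-group comparison of linked change scores intact. It should be fixed, but it does not overturn the main analysis.

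**What to change.** First state which test was run for the within-group comparisons. If it was paired, correct the sentence in the Data Analysis section. If it was independent, replace it with paired t-tests, or with mean change and its 95% CI, in each group. In either case label the within-group results descriptive and rest the effectiveness conclusion on the between-group difference in mean change, which may stay an independent t-test on change scores.

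Add a sentence saying whether and how each mother's pre and post questionnaires were linked.

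If records are linked, the cost is a re-run of the within-group tests in SPSS and one or two changed sentences. If they are not, neither the paired test nor the standard error of the change-score comparison can be computed, and that must be reported as a limitation.

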**Intervention protocol and analysis**

**Date :24/2/2025**

**[name]**

**NCT07069621**

**Intervention Protocol**

The Positive Parenting Program (Triple P), developed by Sanders et al. (2008) at the University of Queensland, Australia, is an evidence-based intervention designed to enhance parent-child interactions. The program equips mothers and caregivers with effective strategies to mitigate behavioural problems in children while boosting their confidence and parenting skills (Ashori, 2023).

An online course from the Triple P Association in Britain was completed by the researcher, leading to an accredited certificate to train in Triple P Level 4(Appendix 4), specifically tailored for children with special needs. The core content for the sessions was sourced from the Triple P provider website and supplemented by additional materials, which the researcher translated into Arabic from Every Parent manual, a key resource in the Triple P curriculum. Each subtopic was reinforced with Arabic-language videos from the Triple P program, shown during the sessions to illustrate key concepts and skills.

The program began with an introductory session, which covered the program's objectives, established a trusting relationship with the participants, and secured informed consent. During this session, demographic data was collected, and pre-intervention questionnaires were completed by the mothers. The implementation of Triple P consisted of multiple sessions including the major subtopic contents of group triple p covered for the participants (Table 3.1), each lasting approximately two hours, covering program strategies, videos, discussions, and follow-up tasks. Mothers received individual phone calls lasting 30-50 minutes, two to three times after the program to reinforce the practical application of Triple P strategies for managing their children's behaviour and to help troubleshoot any challenges. Daily support was provided through short messages and videos via WhatsApp groups, ensuring ongoing engagement with the program content, using prompts

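### No baseline-adjusted estimate is planned: report an ANCOVA beside the change-score comparison, and describe baseline by group in place of equivalence t-tests

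*Combined protocol and SAP*

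**What the plan says.** **Effect of the intervention.** The Data Analysis section states: "Differences in mean change scores between the two groups were used to assess the impact of the intervention relative to standard care". It also tests effectiveness by comparing pre and post scores, within and between groups, with the independent-samples t-test at a two-sided 5% level. The primary analyses cover three domains: parenting practices, parental competence and child behaviour. No covariate, regression, ANCOVA or mixed model is named in the document, and "Sensitivity or subgroup analysis was not conducted".

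**Baseline data exist in both groups.** Under Intervention Protocol, in the introductory session, "pre-intervention questionnaires were completed by the mothers", and "the control group underwent pre-testing, with post-testing conducted two months later".

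**Baseline comparison.** "To assess baseline equivalence between the intervention and control groups, independent samples" t-tests were run on every pre-intervention variable. No consequence is attached to the result. Separately, "Descriptive statistics (frequencies, percentages, means, and standard deviations) were used to characterize demographic variables and baseline measures". The text does not say that these are shown by group.

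**Allocation.** The supplied text does not say how mothers were assigned to Triple P or control. The Pilot Testing section speaks of random selection from a clinic registry, which is sampling and not allocation. It also says that ten mothers were chosen by convenience to receive the programme in the pilot and were kept in the study sample.

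**The concern.** A change score uses the baseline but fixes its coefficient at 1; a comparison of post scores alone fixes it at 0. ANCOVA estimates the coefficient from the data. The plan has the data for this and does not use them.

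What is at stake depends on allocation:

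- **Random allocation.** Precision is given away on data already collected. The change-score comparison remains valid.
- **Non-random allocation.** The change score and ANCOVA rest on different assumptions about how a baseline gap would have evolved without the intervention. They can give different answers, and with only unadjusted results a reader cannot see how far the conclusion depends on that choice.

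The baseline t-tests do not fill the gap. A non-significant test does not show equivalence, so a material difference could be reported as equivalence and pass into the result without adjustment.

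**Working it through.** The document gives no sample size, SD, pre-post correlation or target effect, so there is no stated figure to reproduce. All inputs below are assumptions, shown as ranges. Let SDpre = 1, k = SDpost/SDpre, r = pre-post correlation within group, n = mothers per arm.

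**1. Precision under random allocation**

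Variance per mother:
- change score: 1 + k² − 2rk, which is 2(1−r) at k = 1
- ANCOVA: k²(1−r²), which is 1−r² at k = 1

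At k = 1 the ratio of ANCOVA to change-score variance is (1−r²)/[2(1−r)] = (1+r)/2, so the cut is (1−r)/2. Power and 95% CI half-width below take n = 40 per arm and a 0.5 SD effect. They use the noncentral t and charge ANCOVA a factor 1 + 1/(2n−4) for estimating the slope.

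| r | Change variance | ANCOVA variance | Cut | Power, change → ANCOVA | Half-width (SD), change → ANCOVA |
|---|---|---|---|---|---|
| 0.3 | 1.40 | 0.91 | 35% | 46% → 63% | 0.53 → 0.43 |
| 0.5 | 1.00 | 0.75 | 25% | 60% → 72% | 0.445 → 0.388 |
| 0.7 | 0.60 | 0.51 | 15% | 81% → 87% | 0.345 → 0.320 |
| 0.9 | 0.20 | 0.19 | 5% | 99.9% under both | about 0.20 under both |

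With the slope factor included, the cuts at n = 40 are 34.1%, 24.0%, 13.9% and 3.8%. Simulation at n = 40 gave variance ratios of 0.66, 0.74 and 0.87 at r = 0.3, 0.5 and 0.7, against 0.65, 0.75 and 0.85 in theory.

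Unequal SDs at r = 0.5:
- k = 0.8: 0.48 against 0.84, a cut of 43%
- k = 1.25: 1.17 against 1.31, a cut of 11%
- if rk = 1, there is no gain

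Chance baseline imbalance is not a further cost. At k = 1, 2(1−r) − (1−r²) = (1−r)², which is exactly the extra variance that the imbalance contributes.

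**2. Non-random allocation**

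The ANCOVA estimate minus the change-score estimate is (1−rk) times the baseline gap, or (1−r) times the gap at k = 1. Take no true effect and an intervention group 0.3 SD higher at baseline:

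| r | Post scores follow regression on baseline: change score off by | Group gap is stable: ANCOVA off by |
|---|---|---|
| 0.3 | −0.21 | +0.21 |
| 0.5 | −0.15 | +0.15 |
| 0.7 | −0.09 | +0.09 |
| 0.9 | −0.03 | +0.03 |

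In the first case ANCOVA is about 0; in the second the change score is about 0. Simulation at 40 per arm agrees in both cases.

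**3. What the baseline t-test can detect**

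Power of a two-sided 5% t-test for a true 0.3 SD gap is 21%, 26% and 32% at 30, 40 and 50 per arm. Such a gap would be missed about 79% to 68% of the time.

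**4. Group delivery**

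Steps 1 to 3 assume independent mothers, but Table 3.1 lists five of the eight sessions as group sessions. Assume groups of 10 in the Triple P arm only, with a group effect of 5% or 10% of post-score variance. The variance ratio is then [2(1−r²) + 9·ICC]/[4(1−r) + 9·ICC]. At r = 0.5 this is 1.95/2.45 or 2.40/2.90, so the 25% cut falls to 20% or 17%. In simulation at 40 per arm, false-positive rates were 7.6% or 10.4% for change scores and 8.5% or 12.4% for ANCOVA.

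**The case against.** **The change-score difference is a legitimate estimator.** Under random allocation it is unbiased, and preferring ANCOVA is a matter of efficiency. This stands: no error is alleged in that case, and at high r the gain is small. A reader might infer that the planned test is invalid; the documents do not support that.

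**The change score is not the plan's sole comparison.** A reader might infer that it is. The Data Analysis section also compares pre and post scores between groups, which can be read to include a comparison of post scores. With equal SDs and r between 0 and 1, the ANCOVA estimate lies between the post-score and change-score differences. The accurate statement is that every planned comparison is unadjusted.

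**ANCOVA does not correct the change score if allocation was not random.** This also stands. If the group gap is stable, ANCOVA is the biased estimate, by the same amount. The case for it there is disclosure of both estimates. Nor do the documents show that allocation was non-random: they are silent, and some pages were removed from the supplied text.

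**The section is in the past tense.** An ANCOVA would probably be a post hoc supplement, so the power gain may not be realised. This affects how it is labelled; the second estimate is still informative.

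**The baseline part is presentational.** Means and SDs are already planned, and replacing the tests changes no effect estimate. That is so, but reading a non-significant test as equivalence would still mislead.

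**ANCOVA is slightly more anti-conservative under group delivery.** True on the figures in step 4. Both tests are affected, and clustering needs its own treatment.

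**Conclusion.** The point holds as a recommended addition. All planned comparisons are unadjusted, and no baseline-adjusted estimate is planned although the baseline was measured in both groups.

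- If allocation was random, the loss is one of precision only: 35% to 5% of the variance for r from 0.3 to 0.9 with equal SDs, less or none when r × SDpost/SDpre is close to 1.
- If it was not, the missing information is the sensitivity of the result to the choice of method: 0.21 to 0.03 SD for a 0.3 SD gap over the same range of r, with either method possibly the biased one and neither removing unmeasured confounding.
- The equivalence t-tests cannot give the reassurance that they are used for.

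Confidence is medium, because n, SDs, r, effect and group size are all assumed, and the precision figures take mothers as independent.

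**What to change.** 1. For each outcome, fit an ANCOVA of post score on group with that outcome's baseline score as covariate. Report the adjusted difference with its 95% CI beside the change-score result.
2. If the analysis is already done, label the ANCOVA as added later. Make it the main analysis only if allocation was random and results are not yet known.
3. State how mothers were allocated, including the ten from the pilot. If not at random, give both estimates and say that they rest on different assumptions, can differ by about (1−r) times the baseline gap with equal SDs, and do not remove unmeasured confounding.
4. Replace the equivalence t-tests by baseline means, SDs and standardised differences, by group.

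**Cost.** One SPSS GLM run per outcome, a linearity check, and a short labelled addition to the SAP. Pre and post scores must be linked for each mother, which needs confirming because "all outcome measures were collected anonymously". The pilot mothers' pre and post scores on the PS must come from the same version, since the Pilot Testing section reports a move to a shortened one. Change scores already need both of these. The fix does not deal with group delivery, which has to be handled separately.

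### The between-arm t-test on change scores ignores that Triple P was delivered in groups; group sizes are not reported and the result is not checked at assumed intraclass correlations

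*Combined protocol and SAP*

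**What the plan says.** Under Data Analysis, effectiveness is assessed by "comparing pre- and post-intervention scores within and between groups using independent" t-tests at a two-sided 0.05 level, and the effect measure is given as: "Differences in mean change scores between the two groups were used to assess the impact of the intervention relative to standard care". No group term, robust standard error, design effect or mixed model is mentioned. The same section ends: "Sensitivity or subgroup analysis was not conducted". The intraclass correlation named there is a reliability coefficient for the instruments and has nothing to do with treatment groups.

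Table 3.1 lists sessions 1 to 4 and 8 as two-hour group sessions and sessions 5 to 7 as telephone sessions. The Intervention Protocol adds: "Daily support was provided through short messages and videos via WhatsApp groups". For the other arm it says: "Simultaneously, the control group underwent pre-testing, with post-testing conducted two months later". No group contact is described for controls.

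The number and sizes of the Triple P groups are not stated. Pilot Testing mentions meeting rooms and the later addition of online sessions, but not which groups or sessions were online. The only related count is the 10 pilot mothers who had the sessions and stayed in the study sample; whether they formed one group is not said.

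**The concern.** Mothers who attend the same sessions share discussions, timing and each other's influence, so their change scores may be positively correlated. Controls, as described, have no such shared exposure. This is a partially nested design, with clustering in one arm only. An independent t-test leaves the between-group component out of the intervention arm's variance. Under positive correlation its standard error is too small, its confidence interval too narrow, and its type I error above 0.05.

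This comparison carries the conclusions on parenting practices, parental competence and child behaviour. Without group sizes, a reader cannot judge whether a reported p-value just under 0.05 would survive an allowance for clustering. The point concerns the between-arm test only.

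**Working it through.** **Inputs from the document.** Two-sided alpha 0.05; independent t-test on the difference in mean change; group delivery in the Triple P arm only. No sample size, standard deviation, group size or treatment-group ICC is given, so there is no design figure to reproduce beyond the nominal 0.05.

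**Assumptions.** Equal arms, equal total variance, unclustered controls, stable groups. Group sizes of 5; of 10; and an unequal illustration of 4, 10 and 16. ICC from 0 to 0.10, meaning the correlation of *change scores* between mothers in the same Triple P group.

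**Formulas.**
- Effective group size: m_e = Σm²/Σm. For 4, 10 and 16: (16 + 100 + 256)/30 = 372/30 = 12.4, against a mean of 10.
- Design effect in the Triple P arm: DEFF = 1 + (m_e − 1) × ICC.
- Variance inflation of the between-arm difference: I = (DEFF + 1)/2.
- True type I error of the plain test: 2 × [1 − Φ(1.96/√I)].
- Largest reported p that stays below 0.05 after correction: 2 × [1 − Φ(1.96 × √I)].
- Widening of the confidence interval: √I.

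**Example.** Groups of 10, ICC 0.05: DEFF = 1 + 9 × 0.05 = 1.45; I = 2.45/2 = 1.225; √I = 1.107. Type I error = 2 × [1 − Φ(1.771)] = 0.0766. Threshold = 2 × [1 − Φ(2.169)] = 0.030.

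| Groups | ICC | DEFF | √I | Type I error | Reported p must be below |
|---|---|---|---|---|---|
| any | 0 | 1.00 | 1.000 | 0.0500 | 0.050 |
| 5 | 0.01 | 1.04 | 1.010 | 0.0523 | 0.048 |
| 5 | 0.10 | 1.40 | 1.095 | 0.0736 | 0.032 |
| 10 | 0.01 | 1.09 | 1.022 | 0.0552 | 0.045 |
| 10 | 0.02 | 1.18 | 1.044 | 0.0605 | 0.041 |
| 10 | 0.05 | 1.45 | 1.107 | 0.0766 | 0.030 |
| 10 | 0.10 | 1.90 | 1.204 | 0.1036 | 0.018 |
| 4, 10, 16 | 0.02 | 1.228 | 1.055 | 0.0633 | 0.039 |
| 4, 10, 16 | 0.05 | 1.57 | 1.134 | 0.0838 | 0.026 |
| 4, 10, 16 | 0.10 | 2.14 | 1.253 | 0.1178 | 0.014 |

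**Simulation check** (200,000 null runs, an assumed 30 mothers per arm, ICC 0.02 / 0.05 / 0.10). The plain t-test rejects in 6.1 / 7.7 / 10.4% with three groups of 10, and in 6.3 / 8.4 / 12.0% with groups of 4, 10 and 16. Recomputing the standard error at the true ICC with m_e gives 5.1 / 5.1 / 5.3% and 5.0 / 5.1 / 5.5%. Using the mean size instead of m_e for 4, 10 and 16 gives 5.3 / 5.7 / 6.4%, so m_e is the right quantity.

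**Can the ICC be estimated from the trial?** With k groups of size m, the ANOVA estimate of the group variance is zero or negative with probability P[F(k−1, k(m−1)) ≤ (1 − ICC)/(1 + (m − 1) × ICC)]. For m = 10 and ICC 0.05 the cut-off is 0.95/1.45 = 0.655, and the probability is 47% for 3 groups, 25% for 10 and 14% for 20. With few groups, a fitted model will often report no clustering when there is some.

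**The case against.** The strongest reply is that every figure above is conditional. Group sizes and ICC are assumed, and the 4, 10, 16 split is only an illustration. There are also reasons to expect a low ICC. Only one trained person is mentioned ("An online course from the Triple P Association in Britain was completed by the researcher"), so differences between trainers may not arise. Contact was partly individual ("Mothers received individual phone calls lasting 30-50 minutes, two to three times after the program"), and online sessions were added. At ICC 0.01 with groups of 5 or 10, the type I error is only 5.2% to 5.5%. This stands, and it is why the size of the problem is given as a range that begins at negligible.

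Stable groups are also inferred. Table 3.1 is adapted from a cited source and gives 15 to 30 minutes for the telephone sessions, where the text gives 30 to 50, so it may not record actual delivery; the two passages need reconciling. The WhatsApp groups are not said to match the session groups, and a single arm-wide group would add no between-group variance. This also stands, and it bears on which correction is feasible. It does not justify assuming independence without a check.

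Finally, the assumed-ICC table does not restore an exact 0.05 level, because the true ICC is unknown, and it does nothing about bias from how mothers came to be in each arm. Both points are correct. The table shows how far the conclusion depends on the independence assumption, which a reader cannot currently see.

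**Conclusion.** The concern holds. Group delivery in one arm, a test that assumes independent mothers, unreported group sizes and the absence of any sensitivity analysis are all on the page. What is uncertain is the size: from 5.0% at ICC 0 to about 10.4% at ICC 0.10 with groups of 10, and 11.8% if sizes were as uneven as 4, 10 and 16. These figures rest on equal arms, equal variances, stable groups, unclustered controls and an otherwise valid comparison. A clearly significant result would survive; a reported p between about 0.02 and 0.05 might not. Confidence is medium, because the omission is certain and its consequence is not.

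**What to change.** 1. Report the number and sizes of the Triple P groups, counting the mothers analysed, and which groups or sessions were in person or online.
2. Report each between-arm difference in mean change with its p-value and 95% confidence interval recomputed at assumed ICC 0, 0.02, 0.05 and 0.10. Use variance s1² × (1 + (m_e − 1) × ICC)/n1 + s0²/n0, with arm 1 the Triple P arm and m_e = Σm²/Σm rather than the mean group size. State that the ICC is that of change scores.
3. Add a partially nested mixed model (random group effect in the Triple P arm only, Satterthwaite or Kenward-Roger degrees of freedom) only if membership was stable, can be linked to outcomes, and there are enough groups to estimate the group variance. Ethical consideration says outcomes were collected anonymously, so linkage may be impossible. With few groups, let the assumed-ICC table stand alone.
4. If all mothers formed a single group, say that its effect cannot be separated from the intervention effect.

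The cost is retrieving group sizes, presumably from session records, plus a short extra analysis. No new outcome data are needed, and the table itself needs no linkage of individual outcomes to groups. The interval widens by a factor of 1.00 to 1.20 for equal groups of 10 over ICC 0 to 0.10, and by up to about 1.25 for sizes such as 4, 10 and 16.
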